1.3.1 Expression of PDGFRB is influenced by common gene variant

A review of the literature shows three separate population-based studies that have identified a cisacting protein quantitative trait locus (pQTL) at PDGFRB for circulating levels of PDGFRB reaching genome-wide significance (P-value $<3\times10^{-113}$). We have reproduced this in our PAH cohort (rs2304058 variant, P-value $<1.88\times10^{-92}$) - see Figure 1.

[figure not shown]
Figure 1 - pQTL for PDGFRB

Further analysis shows a 1.6-fold increase in circulating PDGFRB levels per risk allele - see Figure 2. The difference between patients homozygous for the reference and risk alleles is approximately 3.5 standard deviations. If PDGFRB is an important target for Imatinib in PAH, PDGFRB genotype may

influence therapeutic response, or at least the dose required to elicit a response and the risk of dose-limiting side effects.

[figure not shown]
Figure 2 - Relationship of PDGFRB pQTL to plasma PDGFRB levels in PAH patients

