2. STUDY OBJECTIVES

Part 1: To identify the highest tolerated dose of Imatinib (in the range of 100mg and 400mg once daily for 4 weeks) in patients with PAH.

Part 2: To assess the efficacy of Imatinib administered at the highest tolerated dose (once daily for 24 weeks) on PVR in PAH patients according to genes that regulate PDGF activity.

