3. STUDY OUTCOME MEASURES

3.1 Primary outcome measures:

- Part 1: Discontinuation of the drug for more than 5 consecutive days due to Grade 2 or above Adverse Events defined by the National Cancer Institute (NCI) Common Terminology Criteria for Adverse Events (version .5.0, 2017), adapted for this study - see Appendix 2.
- Part 2: The primary efficacy endpoint is a binary variable. For patients with a baseline PVR >1000 dynes·s·cm⁻⁵, success is defined by an absolute reduction in PVR of ≥300 dynes·s·cm⁻⁵ at 24 weeks. For patients with a baseline PVR ≤1000 dynes·s·cm⁻⁵, success is a 30% reduction in PVR at 24 weeks.

3.2 Secondary outcome measures:

- Change in PVR from baseline according to genes that regulate PDGF activity.
- Change in 6MWD at 24 weeks.
- Change in right ventricular ejection fraction (RVEF) values, measured in echocardiogram (at screening assessment and at 24 weeks).
- Change in plasma brain natriuretic peptide (proNT-BNP) levels from baseline at 24 weeks.

• Change in Quality of Life (QoL) scores (23) from baseline at 24 weeks.

3.3 Exploratory outcome measures:

• Change in plasma proteome from baseline at 24 weeks.

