4. INVESTIGATIONAL PLAN

4.1 Overall study design and plan

Patients will be invited to participate by their local designated pulmonary hypertension hospital. Suitable patients will be treated with Imatinib once daily for up to 24 weeks. The study is in two parts. The screening and consenting procedures are the same for Parts 1 and 2.

Part 1 will recruit 6 to 13 patients to identify the highest tolerated dose of Imatinib within the 100mg to 400mg per day range. This dose will then be used in Part 2 in a separate group of patients to assess efficacy according to the genes that relate to PDGF activity. It is necessary to find a single dose to maximise the opportunity to assess variation in response by genotype (i.e. reduce the influence of variation in exposure). It is necessary to find the highest tolerated dose to maximise the opportunity to capture a clinical response (i.e. reduce the chance of missing an effect). A starting dose of 100mg is based on experience from compassionate use; some patients, such as the case report above, have reported benefit from this dose. Doses of 200mg to 400mg daily were investigated in IMPRES (10) and many patients ended up on 200mg daily in the extension study. Our prior model of toxicity -see Section 10; skeleton- predicts that 200mg daily is likely to be the highest tolerated dose in PAH, and Part 1 is designed to explore this. A lower dose will be investigated in the efficacy phase if better tolerated.

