By definition, the highest tolerated dose is reached in this trial when there is a 20% probability that a patient will not be able to continue the drug for 5 consecutive days. All patients who are tolerating Imatinib will be asked to continue on their assigned dose to the end of week 24 and their clinical

response will be measured by the change in PVR (measured through a follow-up RHC). Dose adjustments within the range 100mg to 400mg daily are permitted at the discretion of the responsible physician according to clinical need but if a patient is unable to tolerate 100mg daily, they are withdrawn from the study.

The objective of Part 2 is to define the clinical response to Imatinib after 24 weeks treatment with the highest tolerated dose by measuring the change in PVR through a follow-up RHC. Some patients from Part 1 will have continued on the highest tolerated dose to 24 weeks and so be evaluable for additional efficacy at this dose. Part 2 will continue recruitment of additional patients to a total of 34 evaluable patients; all patients in Part 2 will receive the highest tolerated dose (defined in Part 1) for 24 weeks. Patients will be monitored for safety at the end of Weeks 4, 8, 12 and 24, with telephone assessments at the end of Weeks 16, 20, and 28. If a patient becomes intolerant of Imatinib, they will be allowed to continue with a reduced dose or alterative treatment as guided by their NHS specialist physician, but they will be withdrawn from the study. Beyond that point, we will not be collecting new data from those patients. The clinical response of all patients who complete 24 weeks on the highest tolerated dose of Imatinib will be measured by change in PVR from baseline at Week 24. The primary efficacy endpoint is a binary variable: for patients with a baseline PVR >1000 dynes·s·cm⁻⁵, success is defined by an absolute reduction in PVR of ≥300 dynes·s·cm⁻⁵at 24 weeks; for patients with a baseline PVR ≤1000 dynes·s·cm⁻⁵, success is a 30% reduction in PVR at 24 weeks.

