7.6.3 Genotyping

A mouth swab sample (saliva and buccal cells of maximum 2ml) will be collected for each individual participant at screening. Samples may be temporarily stored at the recruiting site. Samples will be shipped to the accredited laboratory contracted to conduct central laboratory DNA testing. These samples will be analysed by polymerase chain reaction (PCR) using appropriate primers for single nucleotide polymorphisms (SNPs) related to PDGF activity. Sample-related data (labelling information) shared with Imperial College will be pseudonymised (coded). Details on preparation, labelling, storage and shipment of these samples can be found in the relevant section of the laboratory manual.

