Primary analysis of the response rate (PVR reduction after 24 weeks) will be done using an Intention-To-Treat approach. We will provide an alternative Bayesian analysis based on the posterior distribution of the treatment effect of the highest tolerated dose of Imatinib. Treatment effects will be estimated through 95% confidence intervals and credible intervals for the Bayesian analysis using the posterior distribution which results from the data collected and different priors (including a non-informative one). Vague, sceptical and enthusiastic priors will also be considered. The secondary outcomes assessed will be analysed in a similar manner when possible. Secondary analysis will include linear regression models adjusted for potential confounders (e.g., genotype, age, and gender). Continuous data will be summarised with means (geometric means for log-transformed data, otherwise arithmetic), medians, standard deviations, inter-quartile range, coefficient of variation. Categorical data will be summarised by counts per level within factors. In case of missing data, the missing data mechanism will be explored and multiple imputation applied as a sensitivity analysis if appropriate.

[figure not shown]

Figure 6 - Skeleton

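### Section 10 lists genotype as a confounder although Part 2 asks about it as the predictor of change in PVR, and does not name baseline PVR among its example covariates

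*Protocol*

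**What the plan says.** Protocol section 2 sets the Part 2 aim as the efficacy of imatinib "on PVR in PAH patients according to genes that regulate PDGF activity". Section 3.2 lists as its first secondary outcome "Change in PVR from baseline according to genes that regulate PDGF activity". Section 4.1 gives genotype as a reason for the design: "It is necessary to find a single dose to maximise the opportunity to assess variation in response by genotype". The same section adds that "all patients in Part 2 will receive the highest tolerated dose (defined in Part 1) for 24 weeks".

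Section 7.6.3 says the swab samples will be tested for "single nucleotide polymorphisms (SNPs) related to PDGF activity". Section 1.3.1 describes one variant at PDGFRB, rs2304058, on a per-allele scale: "Further analysis shows a 1.6-fold increase in circulating PDGFRB levels per risk allele".

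In section 10, genotype appears once: "Secondary analysis will include linear regression models adjusted for potential confounders (e.g., genotype, age, and gender". The sentence before it promises that "The secondary outcomes assessed will be analysed in a similar manner when possible", which refers back to confidence and credible intervals. Baseline PVR is not among the named covariates, although the list is given by way of example.

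**The concern.** The protocol gives genotype two roles that do not fit together. In the objective, the outcome list and the design rationale it is the variable whose relation to PVR response is to be learned. In the analysis it is a nuisance term beside age and gender.

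A confounder distorts a contrast between exposures. Part 2 has no such contrast, because every patient takes the same dose. In a single-arm regression of change adjusted for genotype, age and gender, the natural target is the mean change, and the genotype coefficient is a by-product. An SAP that followed this sentence faithfully would report that model without presenting the answer to the gene question as its result.

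Baseline PVR matters for a related reason. Genotype groups are not randomised and may start at different PVR levels, and patients who start high tend to fall more. A genotype coefficient for raw change and one conditional on baseline are then different quantities, and the protocol does not say which is meant.

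**Working it through.** **The plan's own figures.** Section 10 gives no figure for the gene question. Its sample size belongs to the overall response rate, and those figures reproduce. Under a true rate of 0.10, the early-stopping probability is 0.9^13 + 13 × 0.1 × 0.9^12 = 0.2542 + 0.3672 = 0.6213. The expected size is 13 + (1 − 0.6213) × 21 = 20.95. The exact two-stage binomial gives type I error 0.0420 and power 0.8034 at 0.27. So 34, the maximum, was not chosen for a genotype comparison.

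**Inputs not in the protocol.** The correlation ρ between baseline and Week 24 PVR, the risk-allele frequency q, and any difference in baseline PVR by genotype are all assumed below and shown over ranges.

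**Relation of baseline to change.** With equal variances at the two visits, the correlation of change with baseline is −√((1 − ρ)/2): −0.50 at ρ = 0.5 and −0.39 at ρ = 0.7.

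**Precision gained by adjustment.** Residual variance with baseline in the model, relative to raw change, is (1 − ρ²) / (2(1 − ρ)) = (1 + ρ)/2.
- ρ = 0.5: 0.75, so the SE ratio is √0.75 = 0.866, about 13% lower.
- ρ = 0.7: 0.85, so the SE ratio is √0.85 = 0.922, about 8% lower.

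These ratios ignore the degree of freedom spent on baseline. Regressing Week 24 PVR or change on genotype and baseline gives the same genotype coefficient, so either outcome will do.

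**Shift when baseline differs by genotype.** Suppose baseline PVR differs by 0.5 SD per allele and genotype has no effect given baseline. The raw-change coefficient then has expectation −(1 − ρ) × 0.5, and the adjusted coefficient has expectation 0.

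**Simulation check.** 4,000 data sets of 34 patients per setting, q = 0.3, in units of the baseline SD. The SE columns have no baseline difference; the coefficient columns have 0.5 SD per allele.

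| ρ | SE, raw change | SE, adjusted | Shift by formula | Mean coefficient, raw change | Mean coefficient, adjusted |
|---|---|---|---|---|---|
| 0.3 | 0.326 | 0.266 | −0.35 | −0.36 | 0.00 |
| 0.5 | 0.274 | 0.243 | −0.25 | −0.25 | 0.00 |
| 0.7 | 0.210 | 0.200 | −0.15 | −0.15 | 0.00 |
| 0.9 | 0.124 | 0.119 | −0.05 | −0.05 | 0.00 |

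The simulated reductions in SE at ρ = 0.5 and 0.7 are about 11% and 5%, a little below the formula because of the lost degree of freedom and simulation error. When baseline does differ by genotype, the two terms overlap and the gain shrinks: SE 0.278 to 0.254 at ρ = 0.5, and 0.214 to 0.212 at ρ = 0.7. In that case the main benefit is removal of the shift.

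**What 34 patients can show.** For an additive allele count, SE = 1/√(34 × 2q(1 − q)) in residual SD units.
- q = 0.1: SE 0.404; 95% half-width 1.96 × 0.404 = 0.79; effect detectable with 80% power (two-sided 5%) 2.80 × 0.404 = 1.13.
- q = 0.5: SE 0.243; half-width 0.48; detectable effect 0.68.

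Even a correctly specified analysis will therefore detect only large genotype effects.

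**The case against.** The strongest reply is that the label is a slip with little consequence. A linear model that includes genotype returns a genotype coefficient and standard error whatever the term is called, and section 10 promises interval estimates for secondary outcomes where possible. The sentence also covers walk distance, natriuretic peptide and quality of life, where genotype as a covariate is unremarkable. The covariate list is only illustrative, and a full list commonly belongs in the SAP, which is not shown.

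Much of this stands. A reader might infer that the gene question has no estimate, or that adjustment removes the gene effect. Neither follows, because adjusting for a covariate does not remove that covariate's own coefficient. A reader might also object that the primary test ignores genotype. That is no error: the primary endpoint is the overall response rate, and the gene outcome is listed as secondary.

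It is also tempting to treat the unlisted SNPs in section 7.6.3 as a multiplicity fault, or to say that 34 patients allow only one test. The protocol gives neither a number of SNPs nor a test level, claims no confirmatory status for any of them, and may leave selection and coding to the SAP. Those readings are not supported.

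The reply does not remove the contradiction in role. That is what the document states, not something left to the SAP, and section 10 has no other sentence on genotype that puts it right.

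**Conclusion.** The point holds as a misstated role and an unstated estimand. Sections 2, 3.2 and 4.1 make genotype the predictor of interest for change in PVR, while section 10 makes it a confounder in a study with nothing to confound. The absence of baseline PVR from the examples is a supporting point, not an error in itself.

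The size is modest. Baseline adjustment lowers the SE by about 8 to 13% before the lost degree of freedom, assuming ρ of 0.5 to 0.7, equal variances and no baseline difference by genotype. If baseline differed by an assumed 0.5 SD per allele, it would also remove a shift of about 0.15 to 0.25 SD at those correlations, provided genotype had no effect given baseline.

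A reader might take the corrected analysis as evidence that genotype modifies the effect of imatinib. It cannot show that. Without a control group, an association with change on imatinib is not separable from a different natural course or regression to the mean.

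**What to change.** In section 10, mirrored in the SAP, add a statement for the first secondary outcome in section 3.2:
- Genotype is the factor of interest.
- Week 24 PVR, or change in PVR, is regressed on genotype with baseline PVR as a covariate.
- The genotype effect is reported with its 95% interval.
- Age and sex enter in a sensitivity model.
- The result is described as an association with change on imatinib, not as effect modification, because there is no control group.

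The existing sentence can stay for the other secondary outcomes. As an option for the SAP, rs2304058 could be named as the main variant, with other SNPs exploratory.

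The cost is a small wording change and one degree of freedom. Genotype and baseline PVR are already collected, and no visit, patient number or primary test changes.

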11. ADMINISTRATIVE AND LEGAL CONSIDERATIONS

11.1 General Legal Requirements

This trial will adhere to the principles outlined in the Medicines for Human Use (Clinical Trials) Regulations 2004 (SI 2004/1031), amended regulations (SI 2006/1928) and the ICH GCP guidelines. It will be conducted in compliance with the protocol, the Data Protection Act and other regulatory requirements as appropriate.

11.2 Ethical and MHRA approvals

This study has Clinical Trials Authorisation from the UK Competent Authority; MHRA. The Study Coordination Centre has obtained approval from an NRES Research Ethics Committee (REC), Health Regulator Authority (HRA). The study must receive confirmation of capacity and capability from each participating NHS Trust before accepting participants into the study or any research activity is carried out. The study will be conducted in accordance with the recommendations for physicians involved in research on human subjects adopted by the 18th World Medical Assembly, Helsinki 1964 and later revisions. A list of the REC members must be provided. If any study staff were present, it must be clear that none of these persons voted. Modifications made to the protocol after receipt of the NRES REC/MHRA approvals must also be submitted as amendments by the site Investigator to the NRES REC/MHRA in accordance with local procedures and regulations.

11.3 Informed consent

Consent to enter the study must be sought from each participant only after a full explanation has been given, an information leaflet offered and time allowed for consideration. Signed participant consent should be obtained. The right of the participant to refuse to participate without giving reasons must be respected. After the participant has entered the trial the clinician remains free to give alternative treatment to that specified in the protocol at any stage if he/she feels it is in the participant's best interest, but the reasons for doing so should be recorded. In these cases the participants remain within the study for the purposes of follow-up and data analysis. All participants are free to withdraw at any time from the protocol treatment without giving reasons and without prejudicing further treatment.

11.4 Patient confidentiality

Participants' identification data will be required for the registration process. The Study Coordination Centre will preserve the confidentiality of participants taking part in the study and is registered under the Data Protection Act.

The site Investigators affirm and uphold the principle of the subject's right to protection against invasion of privacy. Personal health data will be kept confidential.

On eCRFs, paper CRFs or other documents, subjects will be identified by their subject ID only. However, each site Investigator will keep in his/her file a *Subject Identification List*. With respect to the processing of data, every subject has to agree with this in writing. This agreement should be documented together with the written informed consent for trial participation.

11.5 Protocol Amendments

Any changes in the protocol will require a formal amendment. Such amendments will be agreed upon and approved in writing by the site Investigator. Amendments to the protocol will be submitted to the relevant authorities and the NRES REC for approval prior to implementation.

Administrative changes which have no significant impact on the medical or scientific validity of the study will be documented in a statement. The NRES REC will be notified of administrative changes, if applicable.

11.6 Premature Termination of the Trial

The Chief Investigator reserves the right to terminate the trial for well-documented reasons. Instructions will be provided in a separate document should it be determined that assessments beyond those defined by the protocol are required, also on the recommendations of the independent Trial Steering Committee and Data Monitoring Committee.

Further recruitment of subjects will not take place under the following conditions:

- Premature termination of the trial.
- Drug-related events, i.e. SUSARs, emerging AEs that are serious and the risk/benefit ratio is unacceptable.
- Procedure-related events, i.e., the recruitment rate is too low or the number of dropouts for administrative reasons is too high.

• The model predicts that the lowest dose has a toxicity above the TTL with 90% certainty.

11.7 Funder

This project (NIHR128465) is funded by the Efficacy and Mechanism Evaluation (EME) Programme, an MRC and NIHR Partnership. The views expressed in this publication are those of the author(s) and not necessarily those of the MRC, NIHR or the Department of Health and Social Care.

11.8 Sponsor

Imperial College London will act as the main Sponsor for this study. Delegated responsibilities will be assigned to the NHS trusts taking part in this study.

11.9 Indemnity

Imperial College holds Public Liability ("negligent harm") and Clinical Trial ("non-negligent harm") insurance policies which apply to this trial.

11.10 Record Retention

The site Investigator must retain all study records by the applicable regulations in a secure and safe facility. The site Investigator/institution must take measures to prevent accidental or premature destruction of essential documents, that is, documents that individually and collectively permit evaluation of the conduct of a study and the quality of the data produced, including paper copies of study records (e.g. subject charts) as well as any original source documents that are electronic as required by applicable regulatory requirements.

The site Investigator/institution should retain subject identifiers for at least 15 years after the completion or premature termination of the study. Subject files and other source data must be kept for the maximum period of time permitted by the hospital, institution or private practice, but not less than 15 years. These documents should be retained for a longer period, however, if required by the applicable regulatory requirements. It is the responsibility of PI to inform the institution as to when these documents no longer need to be retained.

If a site Investigator moves, withdraws from an investigation, retires, requests to move records to another location or to assign these records to another party or (e.g. other Investigator) who will accept the responsibility, written notice of this transfer must be made to and agreed upon by each party.

11.11 Confidentiality

Imperial College London holds negligent harm and non-negligent harm insurance policies which apply to this study/ Imperial College Healthcare NHS Trust holds standard NHS Hospital Indemnity and insurance cover with NHS resolution for NHS Trusts in England, which apply to this study (delete as applicable).

11.12 Publications

All publications and presentations relating to the study will be authorised by the Trial Management Group. Members of the Trial Management Group and the Data Monitoring Committee will be listed and contributors will be cited by name if published in a journal where this does not conflict with the journal's policy. Authorship of parallel studies initiated outside of the Trial Management Group will be according to the individuals involved in the project but must acknowledge the contribution of the Trial Management Group and the Study Coordination Centre.

